### **8.5.3 Demographic and safety analyses**

For qualitative demographic and safety variables, the population size (N for sample size and n for available data) and the percentage (of available data) for each class of the variable will be presented. Quantitative variables will be summarised using descriptive statistics, including n, mean, SD, median, minimum, and maximum values. Where appropriate, assessments will be summarised by visit. All data will be summarised and listed appropriately.

The number of patients screened and included in the Safety analysis set will be summarised. Demographic and baseline characteristics will be summarised and listed for the Safety analysis set.

Treatment duration will be summarised. Treatment duration is based on the dates of first and last dose.

Study day will be calculated as follows:

- Days prior to first dose: Study day = date – first dose date.
- Days on or after first dose: Study day = date – first dose date + 1.

The “dose” used to determine the first dose date will be fexofenadine for Treatment Period 1, and osimertinib for Treatment Period 2.

Safety profiles will be assessed using the Safety set, in terms of AEs, vital signs (including BP, pulse and temperature), ECG, laboratory data (clinical chemistry, haematology and urinalysis), physical examinations and echocardiogram.

Appropriate summaries of AEs, laboratory data, vital signs, and ECGs will be produced. Adverse events will be summarised separately for Treatment Periods 1 and 2. Laboratory data, vital signs, temperature, and ECGs will be summarised for Treatment Period 2. Summaries will be presented for scheduled visits only. Any unscheduled assessments will be listed. Physical examinations and echocardiogram data will only be listed.

The baseline value for laboratory data, vital signs and ECGs is defined as the latest result obtained prior to the start of Treatment Period 1.

The number of patients experiencing AEs following administration of osimertinib as well as the number of AEs experienced will be summarised. Adverse events will be classified using the Medical Dictionary for Regulatory Activities (MedDRA) system of nomenclature (preferred term and system organ class [SOC]). Adverse events reported before administration of study treatment will be listed only and be referred to as “pre-treatment”. Treatment emergence will be defined for each part of the study (Treatment Periods 1 and 2).

For Treatment Period 1, a treatment emergent AE (TEAE) will be defined as an AE with the start date and time on or after the first dose date and time, and up to (not including) the date and time of the first dose in Treatment Period 2, or up to (and including) 30 days after dosing in Treatment Period 1.

For Treatment Period 2, a TEAE will be defined as an AE with the start date and time on or after the first dose date and time in Treatment Period 2, and up to (and including) 30 days after the last Treatment Period 2 dose date.

Similarly, the number of patients experiencing SAEs, other significant AEs (OAEs), AEs that led to discontinuation of IP (DAEs), AEs that led to death, and treatment-related AEs and the number of such events will be summarised by study period.

All AE data will be listed for all patients. In addition, SAEs, OAEs, and AEs that led to withdrawal or death, and treatment-related AEs will be listed.

Laboratory data (haematology, clinical chemistry and urinalysis) will be summarised and listed. Shift tables will be provided for select tests, where shift from baseline to the worst value for Treatment Period 2 will be summarised. Laboratory data outside the reference ranges should be indicated in the listings.

Concomitant medications will be summarised by the coded terms for both Treatment Periods 1 and 2. The number of patients receiving a medication will be summarised overall and for each period of the study. A medication taken during the course of the study is considered concomitant. A patient is only counted once even if they receive the medication more than once within that period of the study.

The impact of any important protocol deviations, missing data and the use of rescue or concomitant medication on the robustness of study results will be investigated and any methods employed to deal with these will be documented.

Further details of summaries of the safety data will be given in the SAP.

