## **6.1 Definition of adverse events**

An AE is the development of an undesirable medical condition or the deterioration of a pre-existing medical condition following or during exposure to a pharmaceutical product, whether or not considered causally related to the product. An undesirable medical condition can be symptoms (eg, nausea, chest pain), signs (eg, tachycardia, enlarged liver) or the abnormal results of an investigation (eg, laboratory findings, electrocardiogram). In clinical studies, an AE can include an undesirable medical condition occurring at any time, including run-in or washout periods, even if no study treatment has been administered.

The term AE is used to include both serious and non-serious AEs.

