## **6.3 Recording of adverse events**

### **6.3.1 Time period for collection of adverse events**

Adverse events will be collected from the time of signature of informed consent, throughout the PK phase treatment period and including the follow-up period. SAEs will be recorded from the time of informed consent.

For these patients who are continuing to receive osimertinib and are being followed as part of their routine clinical care, AstraZeneca will collect limited information only (see Section 7.8).

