### **6.3.3 Variables**

The following variables will be collect for each AE;

- AE (verbatim)
- The date and time when the AE started and stopped
- Changes in CTCAE grade (for skin reactions and diarrhoea only); maximum CTCAE grade for all other AEs
- Whether the AE is serious or not

- Investigator causality rating against the IP (yes or no)
- Action taken with regard to IP
- Outcome.

In addition, the following variables will be collected for SAEs:

- Date AE met criteria for serious AE
- Date Investigator became aware of serious AE
- AE is serious due to
- Date of hospitalisation
- Date of discharge
- Probable cause of death
- Date of death
- Autopsy performed
- Causality assessment in relation to Study procedure(s)
- Causality in relation to other medication
- Description of AE.

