### **Severity of AE**

It is important to distinguish between serious and severe AEs. Severity is a measure of intensity whereas seriousness is defined by the criteria in Section 6.2. An AE of severe intensity need not necessarily be considered serious. For example, nausea that persists for several hours may be considered severe nausea, but not a SAE unless it meets the criteria shown in Section 6.2. On the other hand, a stroke that results in only a limited degree of disability may be considered a mild stroke but would be a SAE when it satisfies the criteria shown in Section 6.2.

The grading scales found in the revised National Cancer Institute CTCAE Version 4.0 will be utilised for all events with an assigned CTCAE grading. For those events without assigned CTCAE grades, the recommendation is the CTCAE criteria that convert mild, moderate, and severe events into CTCAE grades should be used. A copy of the CTCAE version can be downloaded from the Cancer Therapy Evaluation Program website (<http://ctep.cancer.gov>).

For each episode, the highest severity grade attained should be reported.

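### Period 2 TEAEs are defined by onset alone and grade changes are kept for only two event types, so an AE recorded before osimertinib that worsens on it can be left out of the Period 2 counts

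*Protocol*

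**What the plan says.** Section 6.3.1 sets the start of collection: "Adverse events will be collected from the time of signature of informed consent, throughout the PK phase treatment period". Table 1 and section 4.1 allow screening up to 28 days before the first fexofenadine dose, and the first osimertinib dose follows that fexofenadine dose by 3 to 7 days.

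Section 8.5.3 then sorts AEs by when they begin:

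- Before any study treatment: "Adverse events reported before administration of study treatment will be listed only", under a pre-treatment label.
- Treatment Period 1: onset from the fexofenadine dose and "up to (not including) the date and time of the first dose in Treatment Period 2", or within 30 days of the Period 1 dose.
- Treatment Period 2: "For Treatment Period 2, a TEAE will be defined as an AE with the start date and time on or after the first dose" of that period, through 30 days after its last dose.

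On reporting, the section states: "Adverse events will be summarised separately for Treatment Periods 1 and 2". SAEs, other significant AEs, AEs leading to discontinuation, fatal AEs and treatment-related AEs are also summarised by study period.

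On grades, section 6.3.3 lists what is captured for each AE: "Changes in CTCAE grade (for skin reactions and diarrhoea only); maximum CTCAE grade for all other AEs". Its severity paragraph adds: "For each episode, the highest severity grade attained should be reported". Section 6.1 counts as an AE "the deterioration of a pre-existing medical condition following or during exposure to a pharmaceutical product".

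**The concern.** The safety objective concerns how well osimertinib is tolerated when given with fexofenadine, and CTCAE grading is part of its outcome measure. Period 2 is the only period with osimertinib exposure, so its AE table is the one a reader will use. An onset-only rule leaves out of that table any AE record that was already open at the first osimertinib dose and then became more severe.

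This population makes open low-grade records plausible. Patients have progressed on an EGFR-TKI, which may have been stopped as little as 8 days before study treatment, and they may enter with unresolved Grade 1 toxicity from prior therapy.

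The protocol also treats laboratory data differently. Section 8.5.3 plans shift tables from baseline to the worst Period 2 value, so worsening is counted there but not for AEs.

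**Working it through.** There is no stated figure to reproduce. The check applies the section 8.5.3 rules to example records, then repeats this with a worsening clause added.

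**Inputs**
- Day 0 is the first fexofenadine dose.
- The first Period 2 dose falls on day w, with w = 3 or 7 (washout limits, section 7.2.1).
- The last Period 2 dose is Period 2 Day 41, which is day w + 40. The Period 2 window therefore closes at w + 40 + 30 = w + 70.
- Screening is at most 28 days (section 4.1).

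**Time in which an AE record can open before osimertinib**

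28 + 3 = 31 days to 28 + 7 = 35 days, at most.

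**Rules applied to one continuing record**

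| Onset (day) | Grade increases (day) | Under 8.5.3 as written | With a start-or-worsen clause |
|---|---|---|---|
| −10 | 20 | pre-treatment, listed only | Period 2 TEAE |
| 1 | 20 | Period 1 TEAE only | also a Period 2 TEAE |
| w − 1 | w + 5 | Period 1 TEAE only | also a Period 2 TEAE |
| w + 2 | w + 10 | Period 2 TEAE | Period 2 TEAE (unchanged) |

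The results are the same for w = 3 and w = 7. Only records that open before osimertinib change class.

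**What the stored grade shows**

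For the second row, suppose the event is neither a skin reaction nor diarrhoea, is Grade 1 at onset and reaches Grade 3 on day 20. Section 6.3.3 stores one grade, Grade 3, beside a Period 1 start date. The date on which Grade 3 was reached is not among the listed variables. If the event is diarrhoea, the grade change is recorded, but the onset rule still keeps the event out of Period 2.

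**Size per affected patient**

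1/24 = 4.2 percentage points for that preferred term if all 24 planned patients are in the denominator. With 18 patients it would be 1/18 = 5.6 points. For illustration only, three affected patients of 24 would be 3/24 = 12.5 points. The documents give no basis for how many there will be.

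**The case against.** The strongest reply is section 6.1. Since deterioration of an existing condition during exposure is itself an AE, a worsening on osimertinib could be entered as a new AE starting on the day of deterioration, and the Period 2 rule would then catch it. Sections 5.2.3 and 6.3.6 also call for aggravated examination findings to be reported as AEs. This stands for conditions that predate consent, and for any site that opens a new record on worsening. It does not close the gap for AEs already on record. Nothing requires a second record, and collecting one maximum grade per AE, or per episode, points towards keeping the first.

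Other safeguards are real but partial:
- SAEs carry the date on which they became serious, so their timing can be recovered from listings, though not through the TEAE rule.
- Laboratory worsening has its shift tables.
- All AEs are listed, for a small study.
- Expected progression of cancer signs and symptoms is not an AE (section 6.3.8), which narrows the pool.
- Section 8.5.3 leaves further safety detail to the SAP, which was not available here. An SAP could add a worsening clause and apply it to skin reactions and diarrhoea, assuming their grade changes are dated. For other AEs it cannot recover dates that were never collected.

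A reader might go further and infer four things that the documents do not support:
- That every worsened event is missed. Section 6.1 leaves room for new records.
- That the omitted events are those osimertinib made worse. In an uncontrolled sequential design, worsening after dosing may reflect the disease or an intercurrent illness.
- That the rule always makes osimertinib look safer. The omission can only lower Period 2 counts relative to a start-or-worsen rule, but an overall incidence does not move if the patient has another Period 2 AE.
- That a table will show severe grades under fexofenadine alone. The protocol promises no table of grade by period, so this applies to the record, the listing and any by-grade summary that is later produced.

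**Conclusion.** The point holds in a limited form. Followed as written, sections 8.5.3 and 6.3.3 leave an AE recorded between consent and the first osimertinib dose outside the Period 2 counts when it increases in grade on osimertinib, unless the site chooses to open a new record. For AEs other than skin reactions and diarrhoea, the maximum grade then sits with the earlier onset and the timing of the increase is lost.

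The number of such events cannot be estimated from the protocol. The 4.2 points per patient assumes a denominator of 24, applies to one preferred term, and assumes that the patient has no other Period 2 record of that term. No safety hypothesis test depends on the definition, and the fexofenadine AUC and Cmax analyses are untouched. It should still be changed, because the protocol itself fixes the rule and the missing dates cannot be restored at analysis.

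**What to change.** In section 8.5.3, define a Period 2 TEAE as an AE that starts, or increases in CTCAE grade, from the first Period 2 dose through 30 days after the last Period 2 dose. Use the same start-or-worsen rule for Period 1 within its existing window, so that AEs opened in screening are handled alike. An AE that meets the rule in both periods is counted in both, and any summary by grade should use the maximum grade reached within the period.

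In section 6.3.3, for AEs ongoing at the first dose of a period, record the grade at that time and the date and grade of any later increase. The AE eCRF already takes grade changes for skin reactions and diarrhoea (sections 6.7.1 and 6.7.2), so the same fields can be extended. The alternative is to require a new AE record whenever an ongoing AE increases in grade.

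The cost is a short wording change in two sections and a small extra eCRF entry for AEs ongoing at those doses. No visit, dose or sample changes.

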### **Duration of treatment**

The PK phase consists of a 4-week screening period followed by an approximately 7-week treatment period. The PK phase is further divided into 2 treatment periods which are separated by a 3 to 7 day washout period between fexofenadine doses. During Treatment Period 1, patients will receive a single oral dose of fexofenadine on Day 1. Following a washout period at the end of Treatment Period 1, patients will enter Treatment Period 2. On Day 1 of Treatment Period 2 (Visit 6), each patient will receive a single oral dose of osimertinib 80 mg in combination with a single oral dose of fexofenadine (note that Treatment Period 2 re-starts with “Day 1”). Patients will then receive osimertinib 80 mg once daily from Day 4 to Day 41 inclusive. In addition, patients will receive a single oral dose of fexofenadine on Day 39 (Treatment Period 2).

On completion of the PK phase, patients may continue to take osimertinib tablets as a single agent (continued access phase) if they and the Investigator agree that this is appropriate. Patients should enter the continued access phase immediately on Day 42 after collections of the 72-hour fexofenadine sample (ie, approximately 24 hours after the last dose of osimertinib received in the PK phase) and will receive osimertinib 80 mg once daily for the duration of their participation.

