### PK phase

[figure not shown]
The PK phase is a non-randomised, open-label, 2-period design. Treatment Period 1 and Treatment Period 2 are separated by a 3 to 7 day washout period between doses. A study flow chart for the PK phase is presented in [Figure 1](#). Patients will receive osimertinib 80 mg as a single dose on Day 1 of Treatment Period 2, then 80 mg once daily for 38 days (from Day 4 to Day 41 in Treatment Period 2). Patients will also receive a single oral dose of fexofenadine on Day 1 in Treatment Period 1, and on Days 1 and 39 in Treatment Period 2.

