**Figure 1 Study flow chart**

- a Visit 7 procedures may start on the day of Visit 6 or up to 4 days after Visit 6.  
b Blood samples will be collected for 72 hours after fexofenadine administration.  
c Treatment may commence immediately after the 72 hour blood collection on Day 4 of Treatment Period 1, or an interval of up to 3 additional days may be included; the washout may not exceed 7 days between fexofenadine doses. In Treatment Period 2, from Day 4 (after the 72 hour blood collection, if applicable) until Day 41, patients will receive a daily dose of osimertinib 80 mg.  
d Osimertinib dosing starts on Day 4 after collection of the 72-hour blood samples.  
e Osimertinib 80 mg plus fexofenadine hydrochloride 120 mg administered together on Day 39, followed by osimertinib for 2 additional days. Final fexofenadine blood sample will be collected at 72 hours (on Day 42).  
f For patients who withdraw from the study prematurely and do not go onto continued access.

EGFR epidermal growth factor receptor; EGFRm+ Activating mutations in EGFR; EGFR-TKI EGFR-tyrosine kinase inhibitor(s)

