- Follow-up assessments will only be performed for patients who permanently discontinue osimertinib treatment during the PK phase. On completion of the PK phase, patients may continue to take osimertinib tablets as a single agent until such time as the Investigator believes they are no longer deriving clinical benefit or they stop taking osimertinib for any other reason.
- Compliance with comedication and/or food/beverage restrictions related to CYP3A4 and P-gp activity must be maintained during Day -1 and Day 1.

Clinical Study Protocol  
Drug Substance Osimertinib (AZD9291)  
Study Code D5160C00036  
Version 1.0

C check; D = drug dispensed; ECG electrocardiogram; ECHO echocardiogram; ECOG Eastern Cooperative Oncology Group; HBV hepatitis B; HCV hepatitis C Virus; MUGA multiple gated acquisition scan; P provided; PK pharmacokinetics; R drug returned.

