#### **4.3 Follow-up period**

Those patients who do not proceed into continued access will return to the clinic for follow-up assessments 30 days ( $\pm 7$  days) after their last dose in the PK phase; follow-up assessments are detailed in Table 1.

If the patient's last dose of osimertinib is in continued access (ie, after the PK phase), the patient should be contacted 30 days after their last dose of osimertinib to follow up on any existing SAEs and monitor for new SAEs that may be related to IP.

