## **7.8 Continued Access to Study Treatment**

Patients who have not discontinued osimertinib at the end of the PK phase may continue to receive osimertinib as a single agent, if in the opinion of their treating physician they are continuing to derive clinical benefit from continued treatment (continued access).

After the end of the PK phase, the clinical study database will be closed. No further data will be recorded during continued access other than SAEs that may be related to IP and drug dispensing/accountability, until osimertinib is permanently discontinued. For pregnancy reporting during continued access, see Section 6.6. Investigators will continue to follow up any existing SAEs, and report all SAEs that may be related to IP to AstraZeneca Patient Safety, until 30 days after IP is permanently discontinued, in accordance with Section 6.4 (Reporting of SAEs). Investigators should complete paper SAE forms and fax them directly to the AstraZeneca Patient Safety data entry site for entering onto the AstraZeneca Patient Safety database. Also refer to Section 6.7.3 if an SAE of new or worsening pulmonary symptoms that may be related to IP is reported during the continued access phase.

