#### **9.4 Data management by**

Data management will be performed by AstraZeneca Data Management, according to the Data Management Plan (DMP).

The data collected through third party sources will be obtained and reconciled against study data.

Adverse events and medical/surgical history will be classified according to the terminology of the latest version the Medical Dictionary for Regulatory Activities (MedDRA). Medications will be classified according to the AstraZeneca Drug Dictionary.

Data queries will be raised for inconsistent, impossible or missing data. All entries to the study database will be available in an audit trail.

The data will be validated as defined in the DMP. Quality control procedures will be applied to each stage of data handling to ensure that all data are reliable and have been processed correctly. The DMP will also clarify the roles and responsibilities of the various functions and personnel involved in the data management process.

When all patients have completed the PK phase of the study (or at the request of AstraZeneca), a database lock will be carried out. All PK phase data for patients who have completed by the time of the database lock transfer will be cleaned and validated as defined in the DMP. A CSR will be produced reporting the PK phase data.

Data from continued access phase of the study will only be recorded in the source documents; these data will not be entered into the study database (see also Section 7.8), nor reported as an addendum to the CSR.

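### Period 2 TEAEs are counted to about Day 71, but routine AE capture ends at about Day 42 for patients who continue osimertinib, and the rules on who has the 30-day visit conflict

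*Protocol*

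**What the plan says.** **Window.** Section 8.5.3 lets a Period 2 TEAE start "up to (and including) 30 days after the last Treatment Period 2 dose date". It makes no exception for continued access. The summary measures named there are numbers of patients and numbers of events, with no adjustment for time observed.

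**Dosing and transition.** Section 1.4 describes one osimertinib dose on Day 1 of Period 2, "then 80 mg once daily for 38 days (from Day 4 to Day 41 in Treatment Period 2". The synopsis (Duration of treatment) adds: "Patients should enter the continued access phase immediately on Day 42 after collections of the 72-hour fexofenadine sample".

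**Capture after the transition.** Section 7.8 states: "After the end of the PK phase, the clinical study database will be closed". After that it keeps only SAEs possibly related to the product and drug accountability. The synopsis and Section 1.4 add unexplained sudden deaths and pregnancy outcomes. Section 6.4 puts the SAEs on paper forms. Section 9.4 says of continued-access data that "these data will not be entered into the study database (see also Section 7.8), nor reported as an addendum to the CSR".

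**The 30-day visit.** Section 4.3 says: "Those patients who do not proceed into continued access will return to the clinic for follow-up assessments 30 days". The synopsis (Study design) agrees. The Table 1 footnote says: "Follow-up assessments will only be performed for patients who permanently discontinue osimertinib treatment during the PK phase". The Figure 1 note reads: "For patients who withdraw from the study prematurely and do not go onto continued access". Sections 1.4 and 3.9.1 send any patient who discontinues during the PK phase to the visit.

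**The concern.** The analysis window and the collection rules are both fixed in the protocol, and they do not match. For a continuing completer the window stays open while nothing routine is being recorded. In a table of patient counts, an empty interval looks the same as an event-free one. The patient is still taking osimertinib at that time, so the gap covers on-treatment days.

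A completer who declines continued access can contribute events over the whole window. A Period 2 percentage therefore has no single observation time behind it and shifts with the share of patients who continue. Section 1.2 says the safety data are meant to expand the tolerability database for osimertinib, so the denominator should be interpretable.

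The visit rules are a matter of conduct. A site following one part of the protocol could omit an off-treatment check that another part requires.

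**Working it through.** **Inputs.** Daily dosing Day 4 to Day 41 (Section 1.4); window end at last Period 2 dose + 30 days (Section 8.5.3); entry to continued access on Day 42 (synopsis); Day 39 window of ±3 days (Table 1).

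**The plan's own figure.** 41 − 4 + 1 = 38 daily doses, which matches Section 1.4. The last Period 2 dose is therefore on Day 41.

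**Window against capture.** Window end = 41 + 30 = Day 71. For a continuing completer, capture ends at about Day 42. Unobserved days = 71 − 42 = 29, and 29/71 = 41%. The ratio of window to capture is 71/42 = 1.69. With the ±3-day window the pairs are 68 and 39 days (1.74) or 74 and 45 days (1.64), with 29 days unobserved each time.

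| Patient | Last PK-phase dose | Window ends | Routine capture ends |
|---|---|---|---|
| Completer, enters continued access | Day 41 | Day 71 | about Day 42 |
| Completer, declines, is followed up | Day 41 | Day 71 | up to about Day 71 |
| Stops early, not continuing | Day 30 | Day 60 | Day 60 at most |
| Stops early, not continuing | Day 10 | Day 40 | Day 40 at most |

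The limits in the last two rows are maxima because Section 3.9.1 ends the reporting of new events at the start of another cancer therapy if that comes first. A last dose on Day 12 gives 12 + 30 = 42 days. Earlier stoppers are therefore seen for less time than a continuing completer, and later stoppers may be seen for longer.

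**Illustration only, assuming a constant event hazard.** From 42 to 71 days: p71 = 1 − (1 − p42)^(71/42). A 42-day incidence of 30%, 50% or 70% becomes 45%, 69% or 87%. In the other direction, an event with 30% incidence over 71 days shows as 1 − 0.70^(42/71) = 19.0% over 42 days.

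For the pooled table, let k of 24 patients continue (k is assumed) and all the others be observed for 71 days. The percentage is then [k × 19.0 + (24 − k) × 30]/24:
- k = 6: 27.3%
- k = 18: 21.8%
- k = 24: 19.0%

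**Visit rules side by side.**

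| Place | Who has the 30-day visit |
|---|---|
| Synopsis; Section 4.3 | everyone not entering continued access |
| Table 1 footnote | only those who permanently stop osimertinib during the PK phase |
| Figure 1 note | premature withdrawals not entering continued access |
| Sections 1.4 and 3.9.1 | those who discontinue in the PK phase, with no exception for early transfer to continued access |

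Two patients show the conflict:
- *A completer who declines continued access* has the visit under the synopsis and Section 4.3, but not under the Figure 1 note. Under Table 1 it depends on whether taking the planned final dose counts as stopping during the PK phase.
- *A patient moved early into continued access*, as Sections 3.3 and 6.7 allow, does not have it under the synopsis or Section 4.3. Sections 1.4 and 3.9.1 can be read as requiring it.

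**The case against.** The strongest reply is that Section 8.5.3 only classifies events and sets an upper limit. It does not promise observation to Day 71, and Section 6.3.1 governs collection. This stands in part. Shortening the window alone changes no count for continuing patients, and 42 against 71 days would remain between the two kinds of completer. The crude percentages still need a common basis.

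Section 8.5.3 leaves further detail of the safety summaries to the SAP, and separate lines or rates could be set there. But the window, the collection rules and the visit schedule are fixed in the protocol, and a SAP cannot recover events that were never recorded.

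On the visit, a completer's Day 41 dose falls within the PK phase, so the Table 1 footnote can be read consistently with Section 4.3. That is fair. The Figure 1 note is the clear outlier, since a completer has not withdrawn prematurely.

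Four stronger readings are tempting but not supported:
- *Patients stopping for toxicity get the extra observation.* Section 3.9 lists several reasons for stopping and gives no frequencies. Section 6.7 lets patients with toxicity move straight into continued access, and very early stoppers are seen for fewer than 42 days.
- *The 45/69/87% figures estimate the distortion.* Appendix H says skin effects most often begin in the first two weeks of treatment, so a constant hazard overstates the gap for them.
- *Serious related events are lost.* They still reach the sponsor's Patient Safety database and are absent only from the study's TEAE tables.
- *The database locks on each patient's Day 42.* Section 9.4 ties the lock to all patients completing the PK phase or to a sponsor request. For the individual, routine recording ends on entry to continued access, with the same effect on the table.

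**Conclusion.** The point holds. For a completer who continues, 29 of the 71 days in the Period 2 TEAE window are unobserved while treatment goes on. Across patients, observation runs from well under 42 days to about 71, so a crude Period 2 percentage has no defined observation time. The day counts follow directly from the protocol. The effect on any percentage cannot be fixed from it, because neither the share continuing nor the event timing is given; the percentages above illustrate direction only.

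The visit rules contradict one another for a completer who declines continued access and are unclear for a patient transferred early. It would go too far to infer that completers will miss the visit: that would need a site to follow the Figure 1 note over Section 4.3 and the synopsis.

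The consequence is modest. The trial plans about 24 patients in a single sequence, safety is descriptive with no between-group comparison, and the fexofenadine analysis is unaffected. The correction should still be made, because it is cheap and part of it concerns who has an off-treatment safety check.

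**What to change.** In Section 8.5.3, base the main Period 2 TEAE table on events starting before the first continued-access dose or, for patients who do not continue, before the end of PK-phase treatment. Put the follow-up events of non-continuing patients on a separate line, or give rates per patient-day observed. One of these must accompany the new cut-off, since truncation alone is not enough. State that continued-access events are outside the table.

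Reconcile the synopsis (Study design), Section 1.4, Figure 1, Section 3.9.1, Table 1 and Section 4.3 so that one rule says who has the 30-day visit. That rule should cover completers who decline continued access and patients transferred early. Which rule applies is for the sponsor and investigators to decide.

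The cost is wording in these places and one extra table line, with slightly lower headline TEAE percentages. No new type of visit or sample is needed, because the 30-day visit is already in the plan.
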